3.7 Study Rationale

3.7.1 Rationale for the Tivozanib Dose

In Study KRN951/03-B01, 3 of 8 subjects in the 2 mg tivozanib group experienced a dose limiting toxicity (DLT), indicating that the maximum tolerated dose (MTD) had been exceeded. Based on the results of this study, the MTD was determined to be 1.5 mg/day, and the safety of this dose has been confirmed in multiple subsequent studies.

3.7.2 Rationale for the Tivozanib Dosing Regimen

The initial Phase 1 clinical study (KRN951/03-B01) adopted a dosing regimen with 28-day continuous administration of tivozanib followed by 14-day rest period (during which time no study drug is administered). This study demonstrated that the MTD of tivozanib is 1.5 mg/day, and that toxicities are rapidly reversible upon stopping treatment. The dosing regimen was altered for Study AV-951-07-201 to 21-day (3 weeks) continuous administration of tivozanib followed by 7-day (1 week) rest period during which no study drug is administered. The rationale for changing the dosing regimen was to minimize the rest period during treatment but yet allow subjects to recover from any treatment-related toxicity during the 7-day break. Clinical data with sunitinib have demonstrated that subjects experience recurrence of disease-related symptoms during a 14-day break in treatment [7]. Therefore, the break in tivozanib dosing was reduced from 14-days (Study KRN951/03-B01) to 7 days (Study AV-951-07-201) in an effort to maximize clinical benefit to subjects. The 1.5 mg/day dose given continuously for 21-days followed by a 7-day break has been well tolerated in 272 subjects enrolled in Study AV-951-07-201, and to date only 23 (8.5%) subjects have required a dose reduction and 8 (2.9%) have required a dose interruption. Therefore, this dosing regimen will be used in this Phase 3 study.

3.7.3 Rationale for the Study Design

This is a randomized, controlled, open-label, multicenter study comparing tivozanib to sorafenib in subjects with refractory advanced RCC. Tivozanib has demonstrated significant activity in the second line therapy as described above. Sorafenib was chosen as a comparator for this Phase 3 trial because sorafenib is no longer the most commonly used first line VEGFR inhibitor and is used in advanced RCC. Subjects will be randomized (1:1) to treatment with tivozanib or sorafenib. As differences in such factors as co-medications, prior treatments, and palliative care may affect enrollment rates across the participating centers, the randomization

of subjects will be stratified by the International Metastatic Renal Cell Carcinoma Database Consortium (IMDC) risk category (favorable; intermediate; poor) and prior therapy (two prior VEGFR TKIs; a prior checkpoint inhibitor [programmed cell death -1 protein (PD-1) or PD-1 ligand (PD1-L) inhibitor] plus a prior VEGFR TKI; a prior VEGFR TKI plus any other systemic agent). To protect the integrity of the primary endpoint, progression-free survival will be assessed by an outside group of independent radiology reviewers.

3.7.4 Use in Pregnancy

Tivozanib should not be administered to pregnant women, as it is known that angiogenesis plays an important role in reproductions and embryonic development. It is required that women of childbearing potential undergo a pregnancy test before treatment and must use adequate contraceptive measures while on study and for at least 90 days after the last dose of study drug. Sexually active male subjects must use adequate contraceptive measures, while on study and for at least 90 days after the last dose of study drug. Risk to male sperm is unknown. Effective contraceptive measures include (a) intrauterine device (IUD) plus one barrier method; or (b) 2 barrier methods. Effective barrier measures are male or female condoms, diaphragms, and spermicides (creams or gels that contain a chemical to kill sperm). Oral, implantable, or injectable contraceptives may be affected by cytochrome P450 interactions, and are not considered effective for this study.

**FOR ADDITIONAL INFORMATION, PLEASE REFER
TO THE TIVOZANIB (AV-951) INVESTIGATOR'S BROCHURE**

3.7.5 Potential Risks/Benefits of Therapy With Sorafenib (Nexavar™)

Sorafenib is currently approved for the treatment of advanced RCC and unresectable hepatocellular carcinoma, and locally recurrent or metastatic, progressive differentiated thyroid cancer. Sorafenib was approved in the US on 20 December 2005 as the first VEGF receptor inhibitor for the treatment of advanced RCC. Sorafenib received marketing authorization by the European Commission on 19 July 2006 for the treatment of subjects with advanced RCC who have failed prior interferon-alpha or interleukin-2 based therapy or are considered unsuitable for such therapy. These approvals were based on the demonstration of an improvement in median PFS (sorafenib 167 days [5.5 months]; placebo 84 days [2.8 months]) in a large multinational, randomized, double-blind, placebo-controlled, Phase 3 study of sorafenib vs. placebo, along with a supporting Phase 2, randomized, discontinuation trial in subjects with advanced RCC. Adverse events most frequently observed ($\geq 20\%$) with sorafenib are fatigue, weight loss, rash/desquamation, hand-foot skin reaction, alopecia, diarrhea, anorexia, nausea, and abdominal pain. Overall, the most frequently observed laboratory abnormalities include neutropenia, thrombocytopenia, anemia, lymphopenia, hypophosphatemia, and elevated lipase.

**FOR ADDITIONAL INFORMATION, PLEASE REFER TO APPENDIX E
(SORAFENIB PRESCRIBING INFORMATION) FOR A DESCRIPTION OF
TOXICITIES OBSERVED IN HUMANS TO DATE.**

4 STUDY OBJECTIVES AND PURPOSE

4.1 Primary Objective

The primary objective of this study is as follows:

- To compare the PFS of subjects with refractory advanced RCC randomized to treatment with tivozanib or sorafenib as assessed by blinded independent radiological review (IRR) of computerized tomography (CT) or magnetic resonance imaging (MRI).

4.2 Secondary Objectives

The secondary objectives of this study are as follows:

- To compare the OS of subjects randomized to treatment with tivozanib or sorafenib
- To compare ORR and duration of response (DoR) of subjects randomized to treatment with tivozanib or sorafenib
- To compare the safety and tolerability of tivozanib and sorafenib.

4.3 Tertiary Objectives

The tertiary objectives of this study are as follows:

- To explore any relationship between:
 - tivozanib and sorafenib drug levels and activity
 - tivozanib and sorafenib drug levels and AEs

5 INVESTIGATIONAL PLAN

5.1 Overall Study Design and Plan: Description

This is an open-label, randomized, controlled, multi-national, multi-center, parallel-arm study comparing tivozanib to sorafenib in subjects with refractory advanced RCC. The study is designed to compare the PFS, OS, ORR, DoR, safety and tolerability, of tivozanib and sorafenib.

Subjects will be randomized (1:1) to treatment with tivozanib or sorafenib and stratified by IMDC risk category (favorable; intermediate; poor) and prior therapy (two prior VEGFR TKIs; a prior checkpoint inhibitor [PD-1 or PD1 L inhibitor] plus a prior VEGFR TKI; a prior VEGFR TKI plus any other systemic agent). Once the strata have been identified, treatment will be randomly assigned to a subject within the strata using a complete permuted block design, in an unblinded fashion (open-label). In the event a subject had both 2 TKIs and a checkpoint inhibitor, the subject will be stratified according to the most recent line of therapy.

Subjects must begin treatment with study drug within 14 days after randomization.

5.2 Approximate Duration of Study

It is anticipated that enrollment to this study will be completed in approximately 15 months. A follow-up period of 6 months is expected. Overall duration of subject participation is approximately 24 months.

5.3 Approximate Number of Subjects

Approximately 322 subjects with refractory advanced RCC are planned to participate in this study at approximately 160-190 sites.

Anticipated date of enrollment of first subject: June 2016

Anticipated date of enrollment of last subject: August 2017

Established data cut-off date (targeted number of 242 PFS events): 04 October 2018

5.4 Subject Enrollment

Subject enrollment will take place before the start of study drug administration. Written informed consent must be obtained and all eligibility criteria must be met at the time of enrollment. An Interactive Web Response System (IWRS) will be used for enrollment, randomization and drug management (packaging of clinical supplies, shipping to study sites, and dispensing to subjects).

5.4.1 Subject Enrollment Assignment

Each subject will be assigned a 6-digit identification code. This code will consist of:

- 3-digit site code (Example: 101): assigned by the Sponsor at the time of study initiation.
- 3-digit subject code (Example: 001): assigned by the site via IWRS at the time written informed consent is obtained and screening has begun. Each site will begin with Subject 001.

In the case of re-screening, the same screening number will be used and there is no limit on the number of times re-screening is allowed. There is no window limitation in between the different screening attempts for the same subject.

5.4.2 Treatment Randomization

Once informed consent has been obtained and all eligibility criteria have been met, subjects will be randomized 1:1 to tivozanib or sorafenib using an IWRS. Subjects must begin treatment with study drug within 14 days after randomization. Specific instructions for use of the enrollment/randomization system will be provided in a separate manual.

6 DIAGNOSIS AND MAIN CRITERIA

6.1 Subject Inclusion Criteria

Subjects may be male or female, and must meet all of the following inclusion criteria to be eligible for participation in the study.

1. \geq 18-years of age.

2. Subjects with metastatic RCC who have failed 2 or 3 prior systemic regimens, one of which includes a VEGFR TKI other than sorafenib or tivozanib.
 - a. Postoperative or adjuvant systemic therapy will not be counted as a prior therapy unless recurrence is detected within 6 months of completion of treatment, in which case it will be counted as a prior therapy for metastatic disease.
 - b. Subjects must be off all systemic anti-cancer therapy or radiotherapy for at least 2 weeks prior to Cycle 1 Day 1.
3. Subjects must have recovered from the AEs of prior therapy or returned to baseline. Controlled AEs such as hypothyroidism or hypertension are permitted.
4. Histologically or cytologically confirmed RCC with a clear cell component (subjects with pure papillary cell tumor or other non-clear cell histologies, including collecting duct, medullary, chromophobe, and unclassified RCC are excluded).
5. Measurable disease per the RECIST criteria (Version 1.1, see Appendix A).
6. ECOG performance status of 0 or 1.
7. Life expectancy \geq 3 months.
8. If female and of childbearing potential, documentation of negative pregnancy test prior to enrollment.
9. Ability to give written informed consent and comply with protocol requirements.
10. Sexually active pre-menopausal female subjects (and female partners of male subjects) must use adequate contraceptive measures, while on study and for at least 90 days after the last dose of study drug. Sexually active male subjects must use adequate contraceptive measures, while on study and for at least 90 days after the last dose of study drug. All fertile male and female subjects and their partners must agree to use a highly effective method of contraception. Effective birth control includes (a) IUD plus one barrier method; or (b) 2 barrier methods. Effective barrier methods are male or female condoms, diaphragms, and spermicides (creams or gels that contain a chemical to kill sperm). (Note: oral, implantable, or injectable contraceptives may be affected by cytochrome P450 interactions, and are not considered effective for female subjects in this study.)

6.2 Subject Exclusion Criteria

Subjects meeting any of the following criteria are ineligible for participation in the study.

1. Prior treatment with sorafenib or tivozanib.
2. More than 3 prior regimens for metastatic RCC.
3. Known central nervous system (CNS) metastases other than stable, treated brain metastases. Subjects with previously treated brain metastasis will be allowed if the brain metastasis has been stable by neuroimaging without steroid treatment for at least 3 months following prior treatment (radiotherapy or surgery).
4. Any of the following hematologic abnormalities:
 - Hemoglobin $<$ 9.0 g/dL (packed red blood cell transfusion is permitted)

- Absolute neutrophil count (ANC) < 1500 per mm³
 - Platelet count < 100,000 per mm³.
5. Any of the following serum chemistry abnormalities:
- Total bilirubin > 1.5 × upper limit of normal (ULN) (or > 2.5 × ULN for subjects with Gilbert's syndrome)
 - Aspartate aminotransferase (AST) or ALT > 2.5 × ULN (or > 5 × ULN for subjects with liver metastasis)
 - Alkaline phosphatase > 2.5 × ULN (or > 5 × ULN for subjects with liver or bone metastasis)
 - Creatinine > 1.5 × ULN unless the creatinine clearance is > 40 mL/min. Creatinine clearance can be calculated by standard equations (eg, Cockcroft-Gault) or measured.
6. Significant cardiovascular disease, including:
- Active clinically symptomatic left ventricular failure.
 - Uncontrolled hypertension: Systolic blood pressure > 150 mmHg or diastolic blood pressure > 100 mmHg on 2 or more antihypertensive medications, documented on 2 consecutive measurements taken at least 2 hours apart.
 - Myocardial infarction, severe angina, or unstable angina within 6 months prior to administration of first dose of study drug.
 - History of serious ventricular arrhythmia (ie, ventricular tachycardia or ventricular fibrillation).
 - Cardiac arrhythmias requiring anti-arrhythmic medications (except for atrial fibrillation that is well controlled with anti-arrhythmic medication).
7. Non-healing wound, bone fracture, or skin ulcer.
8. Active peptic ulcer disease, inflammatory bowel disease, ulcerative colitis, or other gastrointestinal condition with increased risk of perforation; history of abdominal fistula, gastrointestinal perforation, or intra-abdominal abscess within 4 weeks prior to administration of first dose of study drug.
9. Serious/active infection or infection requiring parenteral antibiotics.
10. Inadequate recovery from any prior surgical procedure or major surgical procedure within 4 weeks prior to administration of first dose of study drug.
11. Significant thromboembolic or vascular disorders within 6 months prior to administration of first dose of study drug, including but not limited to:
- Symptomatic pulmonary embolism
 - Cerebrovascular accident (CVA) or transient ischemic attack (TIA)
 - Peripheral arterial ischemia > Grade 2

- Coronary or peripheral artery bypass graft.
12. Significant bleeding disorders within 6 months prior to administration of first dose of study drug, including but not limited to:
 - Hematemesis, hematochezia, melena or other gastrointestinal bleeding \geq Grade 2
 - Hemoptysis or other pulmonary bleeding \geq Grade 2
 - Hematuria or other genitourinary bleeding \geq Grade 2.
 13. Currently active second primary malignancy, including hematologic malignancies (leukemia, lymphoma, multiple myeloma, etc), other than non-melanoma skin cancers, non muscle-invasive urothelial cancer, non-metastatic prostate cancer, in situ cervical cancer and ductal or lobular carcinoma in situ of the breast. Subjects are not considered to have a currently active malignancy if they have completed anti-cancer therapy and have been disease free for >2 years.
 14. Pregnant or lactating females.
 15. History of genetic or acquired immune suppression disease such as human immunodeficiency virus (HIV), subjects on immune suppressive therapy for organ transplant.
 16. Life-threatening illness or organ system dysfunction compromising safety evaluation.
 17. Requirement for hemodialysis or peritoneal dialysis.
 18. Inability to swallow pills, malabsorption syndrome or gastrointestinal disease that severely affects the absorption of tivozanib or sorafenib, major resection of the stomach or small bowel, or gastric bypass procedure.
 19. Psychiatric disorder or altered mental status precluding informed consent or necessary testing.
 20. Participation in another interventional protocol.

6.3 Drugs and Other Treatments to be Excluded

The following medications/treatments are prohibited during the study:

1. Chemotherapy, biological therapy (including cytokines, signal transduction inhibitors, monoclonal antibodies), immunotherapy or any other therapy for RCC.
2. Systemic hormonal therapy, with the exception of:
 - Hormonal therapy for appetite stimulation or contraception
 - Nasal, ophthalmic, inhaled and topical steroid preparations
 - Androgen suppression therapy for non-metastatic prostate carcinoma
 - Hormone replacement therapy for conditions such as adrenal insufficiency, hypothyroidism, etc.
 - Low-dose maintenance steroid therapy (equivalent of prednisone \leq 10 mg/day) for other conditions.

3. Treatment with radiotherapy.
4. Herbal preparations/supplements (including daily multivitamin/mineral supplement containing herbal components) or topical ointments containing herbal components.
5. Treatment with strong cytochrome P450 (CYP3A4) inducers or inhibitors (see [Appendix C](#)).
6. Treatment with full dose oral anticoagulants such as warfarin, acenocoumarol, fenprocoumon, or similar agents unless they have been on a stable dose for more than 2 weeks prior to enrollment. Full dose anticoagulation with low molecular weight heparin or unfractionated heparin administered subcutaneously is allowed.

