14.3.1 Study Populations

Three populations will be used in the analyses of the data:

1. The intent-to-treat (ITT) population will consist of all randomized subjects; this population will be used for efficacy analysis, including primary endpoint (progression-free survival). Subjects will be analyzed as randomized.

2. The per protocol (PP) population is defined as all randomized subjects who received at least two cycles (8 weeks) of protocol treatment (unless discontinued due to death or disease progression), have no major protocol deviations that will confound the effects of treatment, and meet all eligibility criteria. Major protocol deviations include but are not limited to failure to satisfy eligibility criteria and taking prohibited medications during the treatment phase of the study. Subjects will be analyzed as treated.
3. The safety population (SAF) will include all subjects who received at least one dose of either study drug. Subjects will be analyzed as treated.

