APPENDIX C CYTOCHROME P450 (CYP3A4) INHIBITORS AND INDUCERS

Cytochrome P450 (CYP3A4) Drug interaction table	
STRONG* INHIBITORS	STRONG* INDUCERS
Ketoconazole	Rifabutin
Nefazodone	Rifampin
Nelfinavir	
Ritonavir	

* Strong inhibition implies that it can cause a > 5-fold increase in the plasma AUC values or > 80% decrease in clearance of sensitive CYP substrates.

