2 DOSAGE AND ADMINISTRATION

The recommended daily dose of NEXAVAR is 400 mg (2 x 200 mg tablets) taken twice daily without food (at least 1 hour before or 2 hours after a meal). Treatment should continue until the patient is no longer clinically benefiting from therapy or until unacceptable toxicity occurs.

Management of suspected adverse drug reactions may require temporary interruption and/or dose reduction of NEXAVAR therapy. When dose reduction is necessary, the NEXAVAR dose may be reduced to 400 mg once daily. If additional dose reduction is required, NEXAVAR may be reduced to a single 400 mg dose every other day [see Warnings and Precautions (5)].

Suggested dose modifications for skin toxicity are outlined in Table 1.

Table 1: Suggested Dose Modifications for Skin Toxicity

Skin Toxicity Grade	Occurrence	Suggested Dose Modification
Grade 1: Numbness, dysesthesia, paresthesia, tingling, painless swelling, erythema or discomfort of the hands or feet which does not disrupt the patient's normal activities	Any occurrence	Continue treatment with NEXAVAR and consider topical therapy for symptomatic relief
Grade 2: Painful erythema and swelling of the hands or feet and/or discomfort affecting the patient's normal activities	1 st occurrence	Continue treatment with NEXAVAR and consider topical therapy for symptomatic relief If no improvement within 7 days, see below
	No improvement within 7 days or 2 nd or 3 rd occurrence	Interrupt NEXAVAR treatment until toxicity resolves to Grade 0–1 When resuming treatment, decrease NEXAVAR dose by one dose level (400 mg daily or 400 mg every other day)
	4 th occurrence	Discontinue NEXAVAR treatment
Grade 3: Moist desquamation, ulceration, blistering or severe pain of the hands or feet, or severe discomfort that causes the patient to be unable to work or perform activities of daily living	1 st or 2 nd occurrence	Interrupt NEXAVAR treatment until toxicity resolves to Grade 0–1 When resuming treatment, decrease NEXAVAR dose by one dose level (400 mg daily or 400 mg every other day)
	3 rd occurrence	Discontinue NEXAVAR treatment

No dose adjustment is required on the basis of patient age, gender, or body weight.

Concomitant strong CYP3A4 inducers: The use of concomitant strong CYP3A4 inducers may decrease sorafenib plasma concentrations and should be avoided (for example, St. John's Wort, dexamethasone, phenytoin).

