carbamazepine, rifampin, rifabutin, phenobarbital). Although a dose increase has not been studied, if a strong CYP3A4 inducer must be co-administered, a NEXAVAR dose increase may be considered. If the dose of NEXAVAR is increased, the patient should be monitored carefully for toxicity [see *Drug Interactions (7.7)*].

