7.7 CYP3A4 Inducers

Continuous concomitant administration of NEXAVAR and rifampicin resulted in an average 37% reduction of sorafenib AUC. Other inducers of CYP3A4 activity (for example, *Hypericum perforatum* also known as St. John's wort, phenytoin, carbamazepine, phenobarbital, and dexamethasone) may also increase metabolism of sorafenib and thus decrease sorafenib concentrations [see *Dosage and Administration* (2)].

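### The strong CYP3A4 inducer list that Section 6.3 cites (Appendix C) is narrower than the one in the protocol's own sorafenib label (Appendix E), and no other rule covers three anticonvulsants

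*Protocol*

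**What the plan says.** Protocol Section 6.3 item 5 prohibits "Treatment with strong cytochrome P450 (CYP3A4) inducers or inhibitors" during the study and gives one cross-reference, to Appendix C. The synopsis repeats the rule and the reference.

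Appendix C is a single two-column "Cytochrome P450 (CYP3A4) Drug interaction table". Its strong-inducer column holds rifabutin and rifampin. Nothing marks the entries as illustrative. The footnote explains strength for inhibitors only: "Strong inhibition implies that it can cause a > 5-fold increase in the plasma AUC values" (or a matching fall in clearance). It gives no test for a strong inducer.

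Appendix E is the sorafenib prescribing information. Its section 2 says: "The use of concomitant strong CYP3A4 inducers may decrease sorafenib plasma concentrations and should be avoided". The drugs it then gives as examples are St. John's Wort, dexamethasone and phenytoin, followed by "carbamazepine, rifampin, rifabutin, phenobarbital". Its section 7.7 reports that rifampicin "resulted in an average 37% reduction of sorafenib AUC", and says that phenytoin, carbamazepine, phenobarbital and dexamethasone, among others, may also lower sorafenib concentrations.

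On the analysis side, Protocol Section 14.3.1 counts "taking prohibited medications during the treatment phase of the study" among the major deviations, and the per-protocol population excludes subjects whose major deviations confound the treatment effect. SAP Section 4.3.2 leaves the definition of major deviations, and of any resulting exclusions, to separate deviation specifications, with final decisions before database lock.

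**The concern.** A site that checks a subject's medication against the only list Section 6.3 cites will not find phenytoin, carbamazepine or phenobarbital. A site that reads Appendix E will find all three described as drugs to avoid with sorafenib. Two sites following the same protocol can therefore reach different answers about the same subject. The situation is plausible: exclusion criterion 3 admits subjects with stable, treated brain metastases and sets a steroid condition for them, but does not mention anticonvulsants.

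Two things are at stake. First, sorafenib is the comparator. If inducer use goes unchallenged in that arm, sorafenib exposure may fall and the comparison could tilt toward tivozanib for a reason unrelated to tivozanib's effect. Second, the coding of prohibited medication may depend on the list consulted. That coding feeds the per-protocol population, which the SAP uses as a sensitivity analysis for primary PFS (Section 4.4) and again in Sensitivity Analysis #1 (Section 4.7.2).

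**Working it through.** The plan states no figure to reproduce here. The check sets the two lists side by side and asks, for each drug in Appendix E section 2, whether Appendix C or another item of Section 6.3 covers it.

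| Drug named in Appendix E section 2 | In Appendix C? | Covered by another 6.3 item? |
|---|---|---|
| Rifampin | Yes | Not needed |
| Rifabutin | Yes | Not needed |
| St. John's Wort | No | Yes, item 4 (herbal preparations) |
| Dexamethasone | No | Largely, item 2 (systemic hormonal therapy), except under its exceptions, such as low-dose maintenance steroid |
| Phenytoin | No | No |
| Carbamazepine | No | No |
| Phenobarbital | No | No |

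Appendix E names 7 drugs and Appendix C carries 2, so 7 − 2 = 5 are missing. Item 4 catches one and item 2 largely catches another, which leaves 5 − 2 = 3 with no other specific cover.

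Could general wording close the gap?

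- **Definition in Appendix C.** It covers inhibition only, so it does not help a site classify an unlisted inducer.
- **Section 7.3.** Medication needed for the subject's welfare is left to the investigator if it is not expected to interfere with evaluation of the study drug. For what is specifically excluded, the section points back to 6.3, and so to Appendix C.
- **Section 13.2.** It sends readers to Appendix E for sorafenib precautions. A site that follows this reference will see the longer list, but 6.3 does not make the link.

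Size of the exposure effect: the documents give one number, the 37% average fall in sorafenib AUC with rifampicin, which Appendix C already lists as rifampin. For the drugs not listed there, Appendix E gives direction only. For tivozanib there are no inducer data.

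Number of subjects: the documents give no rate of use. As an assumption for scale only, take 1% to 5% using one of the unlisted drugs.

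- Both arms: 0.01 × 322 = 3.2 and 0.05 × 322 = 16.1, so about 3 to 16 subjects whose deviation coding could depend on the list.
- Sorafenib arm, the only one with documented reduced exposure: 0.01 × 161 = 1.6 and 0.05 × 161 = 8.05, so about 2 to 8 subjects.

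The documents give no relation between sorafenib exposure and PFS, so these counts cannot be turned into a change in the hazard ratio.

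**The case against.** The strongest reply is that nothing is actually permitted. Item 5 bans the class, Appendix C is a reference aid that never claims to be complete, Section 13.2 directs sites to Appendix E, and Section 7.3 withholds discretion where interference is expected. This stands, and it limits the point to an inconsistency. It does not remove it: the one list cited at the point of use disagrees with the label and offers no test for drugs it omits.

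A second reply is that Appendix E is a product label and not a trial rule. It uses advisory wording, contemplates cases where an inducer must be given, and concerns sorafenib only. Section 7.7 also lists these drugs without the word strong. That is fair, but section 2 of the same label does place them under strong inducers, and the protocol relies on Appendix E for sorafenib drug information (Section 8), management of specific toxicities (Section 10.4.3) and precautions (Section 13.2).

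Four stronger readings are tempting and are not supported:

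- **Subjects in either arm would be undertreated.** The documents describe reduced exposure for sorafenib only.
- **Inducer use would go unrecorded and so distort the Day 15 drug levels unseen.** Sections 7.1 and 7.3 require all concomitant medication to be recorded, prohibited or not. The use may be unflagged, but the data exist.
- **Dexamethasone is as open as the anticonvulsants.** Item 2 restricts systemic steroids apart from listed exceptions, and exclusion 3 requires treated brain metastases to have been stable without steroids for at least 3 months.
- **Per-protocol status certainly flips with the list.** The deviation specifications cited in SAP Section 4.3.2 may already settle the coding, and exclusion also requires that the deviation confound the treatment effect.

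Finally, the change comes late. The data cut-off is 04 October 2018, and SAP Section 4.10 says current patients have been on study for at least a year. An appendix edit would alter little remaining exposure; the value now lies mainly in the data check.

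**Conclusion.** The point holds as an internal inconsistency that should be corrected. Section 6.3 item 5 leads only to a two-drug inducer list, Appendix E names more, and phenytoin, carbamazepine and phenobarbital fall between them with no other specific rule in 6.3.

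Its consequence is conditional. If such use occurred in the sorafenib arm and was not challenged, comparator exposure could have been lower, by an amount the documents do not quantify; the 37% figure belongs to rifampicin and should not be carried over to the other drugs. Deviation coding and per-protocol membership could vary with the list used, unless the deviation specifications already resolve this. The primary analysis is intent-to-treat, so no subject enters or leaves it on this account, and the effect on its result is probably small. That judgement assumes use was uncommon, which the documents neither state nor contradict; the 1% to 5% range is illustrative.

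**What to change.** Reconcile Appendix C, Appendix E (sections 2 and 7.7) and items 2 and 5 of Section 6.3 so that one inducer list governs, including how the steroid exceptions relate to it. Which drugs belong on that list is for the sponsor's clinical team to decide.

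Before database lock, apply the reconciled list to the concomitant-medication data already collected, in the same way in both arms, and use it to code prohibited-medication deviations. Confirm that the deviation specifications cite the same list. Separately, flag every subject who took any inducer named in either appendix, whatever the final list says, so that the number by arm can be reported and the drug-level analyses can take it into account.

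The cost is an appendix edit and one search of coded medications. The downside is a few more recorded deviations and a slightly smaller per-protocol set.
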